8.2.4. Skin-Prick Test

Subjects will have SPTs performed using investigational site- and Sponsor-approved procedures for food allergens. Detailed instructions for performance of the SPT will be provided in the Study Reference Manual. Prior to the SPT, the investigator must ensure that the subject has not

received antihistamine medications for at least 5 half-lives of the medication. Commercial allergenic extract solution is introduced to the epidermis via lancet or skin prick for each of the 15 food sources to determine sensitivity to select foods that may be responsible for triggering symptoms in subjects with FA. In addition to allergens, positive (histamine) and negative (saline-glycerin) controls are also introduced to establish that the response is not blocked and to determine whether there is dermatographism, respectively. The positive and negative control tests should be performed and measured along with the allergen SPT.

8.2.5. Spirometry

Spirometry (FEV₁) and/or PEFR will be conducted in this study, if feasible. Spirometry assesses the integrated mechanical function of the lung, chest wall, and respiratory muscles by measuring the total volume of air exhaled from a full lung, including FEV₁.

In subjects 4 to < 6 years of age, a hand-held peak flow meter (PFM) will be used instead of spirometry. Spirometry is to be attempted in all subjects \ge 6 years of age. For additional instructions, refer to the Study Reference Manual.

For guidance regarding spirometry in a public health emergency, refer to Appendix 6 (Section 10.6).

8.2.6. Pulse Oximetry

Prior to any food challenge or updosing procedure, subjects should have their oxygenation status recorded via pulse oximetry. Subject oxygen status must be > 95% to continue with the food challenge procedure.

8.2.7. Asthma

8.2.7.1. Asthma Severity Assessment

Asthma severity will be assessed by the investigator and documented during screening and at the Week 38 visit using the NHLBI Guidelines for the Diagnosis and Management of Asthma (Expert Panel Report 3 [EPR-3]) (National Asthma Education Prevention Program, 2007; Urbano, 2008). Refer also to Section 10.5.

Any asthma exacerbation events will be reported as AEs or SAEs as appropriate and will be summarized at study conclusion.

8.2.7.2. Asthma Control Assessment

Assessment of asthma control in asthmatic subjects using the Asthma Control Test (ACT) questionnaire (Schatz, 2006) or Childhood Asthma Control Test (C-ACT) questionnaire (Bime, 2016) will be performed as specified in the SoA.

For subjects aged 12 years and older, the ACT has 5 questions, each recorded on a scale of 1 (worst control) to 5 (complete control). The total ACT is the sum of the 5 scores, and ranges from 5 (worst control) to 25 (total control). A total score of 19 or less indicates that asthma is not adequately controlled. Missing data will not be imputed. If any of the 5 questions have a missing response, the total ACT score will not be calculated.

The C-ACT is validated for assessing asthma control in children aged 4 to 11 years (Liu, 2007). It includes 4 questions for the child and 3 questions for the parent to complete. Child responses range from 0 (worst control) to 3 (complete control). Parent responses range from 0 (every day) to 5 (no days). The sum of all 7 questions will make up the total score. The total C-ACT score for subjects under 12 years of age will range from 0 (worst control) to 27 (well controlled). A score of 19 or less indicates uncontrolled asthma. Missing data will not be imputed. If any of the questions have a missing response, the total C-ACT score will not be calculated for that subject.

A listing of the results from the questionnaire, including the total score, will be provided and sorted by treatment group, subject identification, and time point.

8.3. Adverse Events, Serious Adverse Events, and Adverse Events of Special Interest

The definitions of AE, SAE, and adverse event of special interest (AESI) including anaphylaxis can be found in Section 8.3.1, Section 8.3.2, and Section 8.3.7, respectively. The AE severity grading is found in Section 8.3.3 for both allergic AEs (Section 8.3.3.1) and nonallergic AEs (Section 8.3.3.2).

AEs will be reported by the subject and/or legally authorized representative. Subjects will be instructed to complete a daily diary for dosing compliance and to prompt for any reactions after dosing. Symptoms reported by subjects in the diary will be reviewed by site personnel to evaluate for AE reporting.

The investigator and any qualified designees are responsible for detecting, documenting, and recording events that meet the definition of an AE, SAE, or AESI.

The method of recording, evaluating, and assessing causality of AEs and SAEs and the procedures for completing and transmitting SAE reports are provided in Section 8.3.5.2.

Care will be taken not to introduce bias when detecting AEs and/or SAEs. Open-ended and nonleading verbal questioning of the subject is the preferred method to inquire about AE occurrences.

8.3.1. Definition of Adverse Event

AE Definition

An AE is any untoward medical occurrence in a subject temporally associated with the use of study drug during the clinical study, whether or not considered to be related to study drug.
 Note: An AE can therefore be any unfavorable and unintended sign (including an abnormal laboratory finding), symptom, or disease (new or exacerbated) temporally associated with the use of study drug.

Events Meeting the AE Definition

Any abnormal laboratory test results (hematology, clinical chemistry, or urinalysis) or other safety
assessments (e.g., electrocardiogram, radiological scans, vital sign measurements), including those
that worsen from baseline, considered to be clinically significant in the medical and scientific
judgment of the investigator (i.e., not related to progression of underlying disease)

Events Meeting the AE Definition

- Exacerbation of a chronic or intermittent preexisting condition other than the disease under study, including an increase in frequency and/or intensity of the condition
- New conditions detected or diagnosed after study drug administration, even though they may have been present before the start of the study
- Signs, symptoms, or the clinical sequelae of a suspected drug-drug interaction
- Signs, symptoms, or the clinical sequelae of a suspected overdose of either study drug or a concomitant medication. Overdose per se will not be reported as an AE/SAE unless it is an intentional overdose taken with possible suicidal/self-harming intent. Such overdoses should be reported regardless of sequelae.
- "Lack of efficacy" or "failure of expected pharmacological action" per se will not be reported as an AE or SAE. Such instances will be captured in the efficacy assessments. However, the signs, symptoms, and/or clinical sequelae resulting from lack of efficacy will be reported as an AE or SAE if they fulfill the definition of an AE or SAE.

Events NOT Meeting the AE Definition

- Any clinically significant abnormal laboratory findings or other abnormal safety assessments that are
 associated with the underlying disease, unless judged by the investigator to be more severe than
 expected for the subject's condition
- The disease/disorder being studied or expected progression, signs, or symptoms of the disease/disorder being studied, unless more severe than expected for the subject's condition
- For medical or surgical procedures (e.g., endoscopy, appendectomy), the condition that leads to the procedure is the AE.
- Situations in which an untoward medical occurrence did not occur (social and/or convenience admission to a hospital)
- Anticipated day-to-day fluctuations of preexisting disease(s) or condition(s) present or detected at the start of the study that do not worsen

8.3.2. Definition of Serious Adverse Event

If an event is not an AE per the definition above, then it cannot be an SAE, even if serious conditions are met (e.g., hospitalization for signs/symptoms of the disease under study).

SAE Definition

An SAE is defined as any untoward medical occurrence that, at any dose:

Results in death

• Is life-threatening

The term "life-threatening" in the definition of "serious" refers to an event in which the subject was at immediate risk of death at the time of the event. It does not refer to an event that hypothetically might have caused death if it were more severe.

For anaphylaxis to be considered "life-threatening", it should have been assessed as a severity level Grade 4 allergic reaction (refer to Table 11).

Requires inpatient hospitalization or prolongation of existing hospitalization

SAE Definition

In general, hospitalization signifies that the subject has been detained (usually involving at least an overnight stay) at the hospital or emergency ward that would not have been appropriate in the physician's office or outpatient setting. Complications that occur during hospitalization are AEs. If a complication prolongs hospitalization or fulfills any other serious criteria, the event is serious. When in doubt as to whether hospitalization occurred or was necessary, the AE should be considered serious.

- Hospitalization for anaphylaxis should not have been solely for the sake of providing extended
 observation period, such as instances that may be utilized to monitor and manage a biphasic or
 delayed reaction, except in the case of intensive therapy as outlined in "other situations" below.
- Hospitalization for elective treatment of a preexisting condition that did not worsen from baseline is not considered an AE.

• Results in persistent disability/incapacity

The term disability means a substantial disruption of a person's ability to conduct normal life functions.

This definition is not intended to include experiences of relatively minor medical significance, such as uncomplicated headache, nausea, vomiting, diarrhea, influenza, and accidental trauma (e.g., sprained ankle) that may interfere with or prevent everyday life functions but do not constitute a substantial disruption.

Causes a congenital anomaly/birth defect

Other situations:

Medical or scientific judgment should be exercised in deciding whether SAE reporting is appropriate in other situations, such as important medical events that may not be immediately life-threatening or result in death or hospitalization but may jeopardize the subject or may require medical or surgical intervention to prevent one of the other outcomes listed in the above definition. These events should usually be considered serious.

- For an anaphylactic event to be classified as an SAE on the basis of being an "important medical event", it should have resulted in an emergency room visit, and the emergency room visit should have been associated with intensive therapy. The investigator should determine what constitutes "intensive therapy", but this may include interventions such as IV epinephrine, intubation, or admission to an intensive care unit.
 - One or two intramuscular injections of epinephrine should ordinarily not be construed as "intensive therapy".
- If an investigator elects to assess an episode of anaphylaxis to be an "important medical event" when the episode was of mild or moderate severity and did not require intensive therapy, the rationale for the investigator's assessment must be detailed in the event narrative.

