During initial study drug administration and at every subsequent updosing visit at the clinic, subjects with no or mild symptoms will be observed for 2 hours after dosing. For moderate to severe symptoms, the observation period after updosing should be at least 4 hours and up to 24 hours based on symptoms and the treatment regimen needed to stabilize the subject. For allergy symptom severity, refer to Table 11 (Consortium of Food Allergy Research [CoFAR] Severity Grading). For guidance on acute allergy symptom management, refer to the DISP in the Study Reference Manual; the DISP is to be provided to study subjects.

For specific questions related to updosing or continuation of the same dose that are not addressed in the protocol, the investigator should discuss the circumstances with the Study Medical Monitor for decision-making on next steps with regard to study drug.

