6.8.1. Rescue Medications

For allergic reactions to food allergens that may occur during the DBPCFC, subjects will be treated with epinephrine at the discretion of the investigator. Epinephrine is used early during allergic reactions to food allergens to prevent these reactions from becoming more severe. Subjects should already have 2 EAI devices (EpiPen® or equivalent device) with them during the clinical visits (and at all times), but for those who do not, an EAI prescription will be provided at study entry. Study staff must ensure that the subjects/legally authorized representatives have been trained in its proper usage, including injection technique. A periodic refresher of more detailed training for subjects on the FAAP and DISP will occur during the study.

Treatment of allergic reactions during the DBPCFC, study drug dosing, and SPT may also require antihistamines, IV fluids, beta-adrenergic agonist (e.g., albuterol), oxygen, corticosteroids, and/or epinephrine, as indicated. These medicines need to be readily accessible at the study site prior to beginning any DBPCFC, clinic dosing/updosing, or skin-prick testing. See also Table 7 in Section 6.7. Subjects must have access to 2 nonexpired EAIs throughout the study as recommended by the "Revised Anaphylaxis Management Algorithm During the COVID Pandemic" (Food Allergy Research and Education, 2020) and general good practices.

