4.3. Safety Endpoints

The safety endpoints of the study are:

- Incidence of adverse events (AEs)
- Incidence of serious adverse events (SAEs)

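### As worded in Protocol 8.3.2, a Grade 3 anaphylaxis given intensive therapy at the study site, without admission or emergency room transfer, misses an SAE criterion that the same event meets in an emergency room

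*Protocol*

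**What the plan says.** Protocol 8.3.2 opens the important-medical-event route with a general rule: "Medical or scientific judgment should be exercised in deciding whether SAE reporting is appropriate in other situations". It adds that events which may need intervention to prevent a serious outcome are usually to be treated as serious. Nothing in that lead-in mentions place of care.

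For anaphylaxis a narrower test follows: "it should have resulted in an emergency room visit, and the emergency room visit should have been associated with intensive therapy". What counts as intensive therapy is left to the investigator, with the guide that "this may include interventions such as IV epinephrine, intubation, or admission to an intensive care unit". One or two intramuscular epinephrine injections ordinarily do not count. The last bullet concerns the narrative required of investigators who elect this route for weaker cases: "when the episode was of mild or moderate severity and did not require intensive therapy, the rationale for the investigator's assessment must be detailed".

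The other routes in the same section are narrowed for anaphylaxis too. To be life-threatening, "it should have been assessed as a severity level Grade 4 allergic reaction". Hospitalization purely for extended observation does not count, unless intensive therapy was involved.

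Meanwhile the plan has sites treat reactions themselves. Section 6.8.1 lists the treatments that may be needed, including epinephrine, IV fluids and oxygen, and says: "These medicines need to be readily accessible at the study site prior to beginning any DBPCFC, clinic dosing/updosing, or skin-prick testing". Under 6.5.1, for moderate to severe symptoms, "the observation period after updosing should be at least 4 hours and up to 24 hours". Section 10.4.1 makes sites responsible for handling anaphylaxis, with ready access to emergency services and hospital admission.

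**The concern.** A seriousness criterion should turn on what happened to the subject. This one also turns on whether the subject passed through an emergency room. The first dose at each new level and every food challenge are given at sites equipped to treat reactions, so on-site treatment without an emergency room visit is a foreseeable course.

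Three things depend on the label. SAE incidence is a named safety endpoint (SAP 4.3). SUSAR assessment is described for SAEs (Protocol 8.3.6). SAP 7.9.1 also plans separate rows for treatment-emergent SAEs related to study drug, due to accidental exposure and due to food challenge. Challenges take place on site by design and accidental exposures generally do not, so a criterion tied to the emergency room can apply differently across those rows.

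**Working it through.** No arithmetic applies. The check is to take the same reaction through the criteria of Protocol 8.3.2 in two settings.

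| Case | Treated in an emergency room | Treated at the site, no emergency room visit |
|---|---|---|
| 1. Grade 4 | SAE (life-threatening) | SAE (life-threatening) |
| 2. Inpatient admission, including intensive care | SAE (hospitalization) | SAE (hospitalization) |
| 3. Intubated | SAE | SAE if Grade 4 or admitted, which is likely but not automatic |
| 4. Grade 3, intensive therapy, not admitted | Meets the important-medical-event criterion | Criterion not met; SAE only by investigator judgment |
| 5. Grade 1 to 3, one or two intramuscular epinephrine doses, not admitted | Ordinarily not an SAE | Ordinarily not an SAE |

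Setting changes the result in case 4, and in case 3 only when the event is neither Grade 4 nor admitted.

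For case 4 on site, each route in turn:
- Life-threatening fails, because the grade is 3.
- Hospitalization fails, because by the terms of the case there was no admission.
- Important medical event fails as worded, because there was no emergency room visit.
- The lead-in points the other way: an event that needed such intervention would usually be serious.
- The last bullet does not settle it. It deals with mild or moderate episodes without intensive therapy and is silent on a more severe episode that had it.

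What does not depend on the SAE label:
- Every anaphylactic event is an AESI and must be assessed for seriousness (Protocol 8.3.7). That assessment refers back to 8.3.2, so it does not close the gap.
- AESIs and SAEs have the same 24-hour reporting time to the sponsor (Protocol Table 12).
- The study-level stopping rule for anaphylaxis uses CoFAR Grade 4 (Protocol 7.1.1).
- Anaphylaxis of Grade 3 or higher is shown in all AESI tables (SAP 7.9.1).

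**The case against.** The strongest reply is that the criterion is not absolute. It says should, it sits under a call for judgment, and the last bullet presumes that an investigator may elect important-medical-event status when the two-part test is not met. A reader might infer from the emergency room sentence that an on-site reaction can never qualify by this route. The documents do not support that. What remains is that a correct classification depends on each investigator departing from the one criterion the protocol states for anaphylaxis, and investigators may not all do so.

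A reader might also take the dividing line to be home versus site. It is not. A site reaction transferred to an emergency room for intensive therapy qualifies, and a home reaction given one or two intramuscular injections ordinarily does not. Grade 4 events and admissions count in any setting.

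The affected case is narrow. Admission to intensive care meets the hospitalization route, and intubation usually would meet that route or Grade 4. At a hospital-based site, a long observation stay after intensive therapy might itself be read as hospitalization, since 8.3.2 resolves doubt on that point toward serious. Section 6.8.1 lists epinephrine and IV fluids but does not state IV epinephrine. These points limit how often the gap can arise. They do not close it, because the investigator decides what intensive therapy is and no wording covers such therapy given on site.

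Finally, the event is visible elsewhere: in AESI tables, in summaries of epinephrine use (SAP 7.8.3.6) and in maximum symptom severity at challenges (SAP 7.8.3.9). That stands. The safety profile is not hidden. The exposed parts are the SAE endpoint and SUSAR assessment, and the effect on the latter also depends on expectedness information that is not in these documents.

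**Conclusion.** The point holds in a narrow form. As written, a Grade 3 anaphylaxis given intensive therapy on site, with no admission and no emergency room visit, misses a criterion that the same event meets in an emergency room. The condition conflicts with the lead-in of its own section and can make SAE and treatment-emergent SAE incidence, and SUSAR assessment, depend on place of care.

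Its size cannot be estimated, because the documents give no rate for such events. It may be small. A reader might try to size it from Table 3: if all 24 low-dose and 24 high-dose ADP101 subjects reach target, there are 24 × 9 + 24 × 11 = 216 + 264 = 480 supervised first doses. That counts exposures, not affected events, and does not measure the problem.

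A reader might also extend the point to Screening challenges. Reactions there precede the first dose, so under the definition in SAP 7.9.1 they cannot enter treatment-emergent SAE tables. They fall only within SAE collection, which runs from consent (Protocol Table 12). For the treatment-emergent tables, updosing visits and Exit challenges are what matter.

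The conclusion assumes that investigators apply the anaphylaxis criterion as stated and that some events receive intensive therapy on site without transfer or admission. It implies no failure of 24-hour reporting or of the stopping rule.

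**What to change.** In Protocol 8.3.2, reconcile the anaphylaxis bullet with the lead-in. Replace the emergency room condition with one that the event required intensive therapy, as already described there, wherever it was given, including at the study site. This changes classification only and leaves treatment untouched.

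Before database lock, query every AESI anaphylaxis record that shows intensive therapy on site and has no SAE flag, and ask the investigator to reassess seriousness under the reconciled wording. The query matters because Protocol 2.3.2 reports 73 subjects already randomized by March 2022, so amended text alone would not reach events already recorded.

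The cost is a small protocol amendment with IRB/IEC approval (Protocol 10.1.1), one data query, and possibly a slightly higher SAE count.

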8.3.3. Classification of an Adverse Event

8.3.3.1. Allergic Reaction Adverse Event Severity Grading

Allergic reactions will be graded according to the CoFAR grading system for allergic reactions, including events that meet the definition for anaphylaxis (Table 11). This approach is consistent with other industry studies in FAs (Vickery, 2018).

Table 11: CoFAR Severity Grading System for Allergic Reactions

Grade 1: Mild	Grade 2: Moderate	Grade 3: Severe	Grade 4: Life-Threatening	Grade 5: Death
Transient or mild discomfort (< 48 h), no or minimal medical intervention/therapy required. These symptoms can include pruritus, swelling or rash, abdominal discomfort, or other transient symptoms.	Symptoms that produce mild to moderate limitation in activity. Some assistance might be needed, but no or minimal intervention/ therapy is required. Hospitalization is possible. These symptoms can include persistent hives, wheezing without dyspnea, abdominal discomfort/ increased vomiting, or other symptoms.	Marked limitation in activity. Some assistance is usually required; medical intervention/therapy required, and hospitalization is possible. Symptoms can include bronchospasm with dyspnea, severe abdominal pain, throat tightness with hoarseness, and transient hypotension, among others. Parenteral medication(s) are usually indicated.	Extreme limitation in activity. Significant assistance is required; significant medical/therapy is required. Intervention is required; hospitalization is probable. Symptoms might include persistent hypotension and/or hypoxia with resultant decreased level of consciousness associated with collapse and/or incontinence or other life-threatening symptoms.	Death.

Abbreviations: CoFAR = Consortium of Food Allergy Research.

Source: (Jones, 2017b).

